4.2 Primary Effectiveness Endpoint

Objective: To assess effectiveness of using CorPath GRX for robotic-assisted endovascular procedure.

Hypothesis:

$H_0: p \leq 80\% \text{ (90\% - 10\% NI margin)}$

$H_a: p > 80\%,$

where p =proportion of patients with a successfully completed endovascular procedure.

Endpoint: The proportion of subjects with successful completion of the robotic-assisted endovascular procedure absent any unplanned conversion to manual for guidewire or microcatheter navigation, embolization coil(s) or intracranial stent(s) deployment, or an inability to navigate vessel anatomy.

Subjects to Include: Analysis Cohort

Statistical Analysis: The proportion of subjects with a successful procedure completion as defined will be summarized along with a 2-sided Clopper Pearson Exact 95% confidence interval. If the lower bound is greater than 80%, we will declare success and conclude that effectiveness is not inferior to the performance goal of 80%.

4.3 Primary Safety Endpoint

Objective: To assess safety of using CorPath GRX for robotic-assisted endovascular procedure.

Hypothesis:

$H_0: p \geq 15\% (5\% + 10\% \text{ NI margin})$

$H_a: p < 15\%,$

where p =proportion of patients with a safety event.

Endpoint: The proportion of subjects with a safety event where a safety event is intra- and peri-procedural events, including target aneurysmal rupture, vessel perforation or dissection, and thromboembolic event with neurological decline within 24 hours post-procedure or hospital discharge, whichever occurs first.

Subjects to Include: Analysis Cohort

Statistical Analysis: The proportion of subjects with a safety event as defined will be summarized along with a 2-sided Clopper Pearson Exact 95% confidence interval. If the upper bound is less than 15%, we will declare success and conclude that safety is not worse than the performance goal of 15%.

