## PRIMARY SAFETY END- POINT

The primary safety endpoint will be a composite of intra- and peri-procedural events, defined as vascular injury including intra-procedural aneurysm rupture caused by robotically controlled catheters, wires, or devices and thromboembolic events with neurological decline (NIHSS score change  $\geq 4$ ) within 24-hours post- procedure or hospital discharge, whichever occurs first.

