#### 3.3 Primary Safety Endpoint

The primary safety endpoint will be a composite of intra- and peri-procedural events, defined as vascular injury including intraprocedural aneurysm rupture caused by robotically controlled catheters, wires, or devices and thromboembolic events with neurological decline (NIHSS score change  $\geq 4$ ) within 24-hours post-procedure or hospital discharge, whichever occurs first.

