### 6.2 Analysis of Primary Safety Endpoint

The primary safety endpoint will be a composite of intra- and peri-procedural events, including target aneurysmal rupture, vessel perforation or dissection, and major stroke within 24-hours of post-procedure or discharge, whichever occurs first. The proportion of subjects with a safety event as defined will be summarized along with a 2-sided 95% exact binomial confidence interval to demonstrate that safety not inferior to a performance goal based upon historical rates from the literature for comparable procedures.

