## 6.5 Primary Analysis

The goal of the primary analysis will be to demonstrate that cerebral aneurysm coiling treated with CorPath GRX is as effective and safe as compared to the combined historical control treatments for cerebral aneurysm coiling treated with traditional manual operation.

For safety, if the upper bound of the 2-sided 95% confidence interval is less than the performance goal of 15%, we will conclude that the Corindus GRX system did not negatively impact safety.

For performance, if the lower bound of the 95% confidence interval for the proportion of successful patients is greater than the performance goal of 80%, we will conclude that the Corindus GRX system did not negatively impact performance.

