## 13. DEFINITIONS

TERM	DEFINITION
Adverse Event (AE)	Any untoward medical occurrence, unintended disease or injury, or untoward clinical signs (including abnormal laboratory findings) in subjects, users or other persons, whether or not related to the investigational medical device.
Device-Related Adverse Event	Event has a strong temporal relationship to the study device, and alternative etiology is less likely.
Major Stroke	A stroke, which increases the NIHSS of the subject by $\geq 4$ .
Minor Stroke	A stroke, which increases the NIHSS of the subject by $\leq 3$
Transient Ischemic Attack (TIA)	A transient episode of neurologic dysfunction caused by focal brain, spinal cord, or retinal ischemia without acute infarction.
Modified Rankin Scale (mRS)	Scale for measuring general neurologic function. 
 
0. No symptoms at all
 
1. No significant disability despite symptoms; able to carry out all usual duties and activities
 
2. Slight disability; unable to carry out all previous activities, but able to look after own affairs without assistance
 
3. Moderate disability; requiring some help, but able to walk without assistance
 
4. Moderately severe disability; unable to walk without assistance and unable to attend to own bodily needs without assistance
 
5. Severe disability; bedridden, incontinent and requiring constant nursing care and attention
 
6. Dead
 

NIHSS Scale	The National Institutes of Health Stroke Scale, or NIH Stroke Scale (NIHSS) is a tool used by healthcare providers to objectively quantify the impairment caused by a stroke . The NIHSS is composed of 11 items, each of which scores a specific ability between a 0 and 4. For each item, a score of 0 typically indicates normal function in that specific ability, while a higher score is indicative of some level of impairment.  The individual scores from each item are summed in order to calculate a patient's total NIHSS score. The maximum possible score is 42, with the minimum score being a 0
Neurological Deterioration	Defined as $\geq 4$ -point increase compared with baseline in the NIHSS at discharge.
Procedural Related Adverse Event	Defined as events that occur from the endovascular robotic procedure, irrespective of the device.

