Stroke	
A focal neurological deficit of presumed vascular origin persisting more than 24-hours from symptom onset AND a neuro-imaging study or other quantitative study that does not indicate a different etiology. The 24-hour criterion is excluded if the subject undergoes cerebrovascular surgery or dies during the first 24-hours of symptom onset.
 
The definition includes subjects presenting with clinical signs and symptoms suggestive of subarachnoid hemorrhage, intracerebral hemorrhage, or cerebral infarction. The definition also includes sudden loss or worsening of visual acuity due to retinal artery occlusion or retinal emboli.
 
The definition excludes slowly progressive cranial nerve palsies or progressive visual field deficits due to continued aneurysm growth. The definition also excludes stroke events in cases of blood disorders such as leukemia or external events such as trauma.
 
Stroke severity will be graded by the Investigator as major or minor:
 
 
• Major Stroke: A stroke which increases the NIHSS of the subject by <math>\geq 4</math>.
 
• Minor Stroke: A stroke, which increases the NIHSS of the subject by <math>\leq 3</math>.
 
• TIA: a transient episode of neurologic dysfunction caused by focal brain, spinal cord, or retinal ischemia without acute infarction
 

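### The primary safety endpoint is worded in three ways with different listed events, and the available text does not say which wording governs the 15% test

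*SAP*

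**What the plan says.** Three wordings are current in the body text.

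- **Protocol Summary and Section 3.3.** "vascular injury including intraprocedural aneurysm rupture caused by robotically controlled catheters, wires, or devices and thromboembolic events with neurological decline", with an NIHSS change of at least 4, up to 24 hours or discharge, whichever is first.
- **Protocol 6.2.** Events "including target aneurysmal rupture, vessel perforation or dissection, and major stroke within 24-hours of post-procedure or discharge, whichever occurs first". There is no causal condition. Section 13 defines major stroke as a stroke that raises the NIHSS by at least 4, and its stroke definition covers "clinical signs and symptoms suggestive of subarachnoid hemorrhage, intracerebral hemorrhage, or cerebral infarction".
- **SAP 4.3.** Events "including target aneurysmal rupture, vessel perforation or dissection, and thromboembolic event with neurological decline within 24 hours post-procedure or hospital discharge", whichever is first. There is no causal condition and no NIHSS cut-off.

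Protocol 6.5 sets the decision rule without restating the event: "For safety, if the upper bound of the 2-sided 95% confidence interval is less than the performance goal of 15" per cent, safety is declared not to have been harmed. SAP 4.3 attaches the same rule to its own wording. On how the two documents relate, Protocol 6.7 says only that a separate SAP will give further detail on the planned analyses.

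The 5% behind the goal comes from the MAPS table in Protocol 6.4 and SAP 3.1: 30/626, rounded up.

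**The concern.** This is one of the trial's two confirmatory tests, in an open single-arm study with no control group to absorb a change of definition. Adjudicators working from Protocol 3.3 or 6.2 and an analyst working from SAP 4.3 could reach different counts from the same patients. The choice of wording could also be made after the events are known.

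The direction matters too. The benchmark has no robotic-cause filter and includes haemorrhagic strokes. Filtering by cause, or leaving haemorrhagic stroke out, can only lower the trial's rate against a goal that was built without those restrictions.

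**Working it through.** **1. Side-by-side reading of the listed events**

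| Event | Summary / Protocol 3.3 | Protocol 6.2 | SAP 4.3 |
|---|---|---|---|
| Rupture, robotically controlled device | named | named | named |
| Rupture, manually controlled device | not named | named | named |
| Thromboembolic event, NIHSS increase ≥4 | named | named if it meets the stroke definition | named as decline, no cut-off |
| Haemorrhagic stroke, NIHSS increase ≥4, no rupture, perforation or dissection | not named | named | not named |

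A manually caused rupture is foreseeable. Protocol 4.8.5 has manual catheter steps, 4.8.7 allows conversion to manual, and 6.4 plans for about 10% unplanned conversion.

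**2. The plan's own sample size**

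Inputs from Protocol 6.6: p0 = 0.15, p1 = 0.05, power 90%. The two-sided 95% interval gives one-sided 0.025.

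n = [(1.960·√(0.15·0.85) + 1.282·√(0.05·0.95)) / 0.10]² = 95.87, rounded up to 96. The stated figure reproduces. The exact Clopper-Pearson rule at n=96 (pass with at most 7 events) has power 89.2%.

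**3. The benchmark**

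2 ruptures + 21 ischaemic strokes + 7 haemorrhagic strokes = 30, and 30/626 = 4.79%, used as 5%. The table note says the 7 exclude haemorrhagic strokes due to rupture. This event set is closest to Protocol 6.2. No wording matches it exactly: the benchmark does not list dissections, which 6.2 and SAP 4.3 count, and its strokes show no NIHSS cut-off.

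**4. The pass boundary (exact 95% upper limits)**

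- n=108: 8 events give 14.07% (pass); 9 give 15.23% (fail).
- n=120: 10 events give 14.79% (pass); 11 give 15.81% (fail).

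**5. Chance that the wording reverses the result at n=108**

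Let X be the count under the wider wording, Binomial(108, p). Let Y ≤ X be the count under a narrower wording that misses a share f of those events, Binomial(108, p(1−f)). A reversal means X ≥ 9 and Y ≤ 8, so its probability is P(Y≤8) − P(X≤8).

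At the planned p = 0.05, P(X≤8) = 0.9081. The documents do not give f, so these shares are assumptions, expressed as parts of the 30 benchmark events:

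| f | P(Y≤8) | Reversal |
|---|---|---|
| 1/30 | 0.9217 | 1.4% |
| 2/30 (all benchmark ruptures) | 0.9340 | 2.6% |
| 3.5/30 | 0.9500 | 4.2% |
| 7/30 (all benchmark haemorrhagic strokes) | 0.9767 | 6.9% |

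As f approaches zero, so does the reversal probability.

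**The case against.** **The lists may be open.** Protocol 6.2 and SAP 4.3 both introduce their lists with an inclusive word, and Protocol 3.3 speaks of vascular injury in general. A manually caused rupture could count under 3.3 if the robotic condition is only an illustration. Some intracranial haemorrhages could count as vascular injury, and bleeding from rupture or perforation already counts under SAP 4.3. This stands as far as it goes: a reader might infer that the wordings are certain to give different counts, and the documents do not show that. But open wording leaves the count to interpretation; it does not reconcile the three lists.

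**The SAP may govern.** Protocol 6.7 assigns analysis detail to the SAP, and only SAP 4.3 joins a definition to the 15% rule. An analyst would probably follow it. Still, Protocol 6.2 defines the event for the same test, the adjudication sections (5.8 and 9.2) name no wording, and SAP 4.3 lacks the cut-off. Some pages were not available for review, so the absence of a precedence rule is established only for the text at hand.

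**The NIHSS gap is mostly omission.** Protocol 3.3 and Section 13 use at least 4, and SAP 4.4.1 uses the equivalent more than 3. That is fair. The nearest defined term, Neurological Deterioration, is an increase "compared with baseline in the NIHSS at discharge", which misses the endpoint window when discharge comes after 24 hours.

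**The 7/30 share is borrowed.** The MAPS trial had 36.4% ruptured aneurysms; this trial enrols unruptured aneurysms only. The table gives no time window or NIHSS cut-off for the 7 strokes, and some may be perforation bleeds that SAP 4.3 counts anyway. This objection stands, so 7/30 is an extreme upper end.

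**Conclusion.** The three wordings list different events for one confirmatory endpoint, and the available text does not choose between them. The plan should be corrected, but the statistical effect is small: 1.4% to 6.9% reversal probability at the planned 5% rate, for assumed discordant shares of 1/30 to 7/30, and only when the count lies near 8 or 9 of 108. The sample size itself is not in error.

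Three stronger inferences are not supported:

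- **Large reversal probabilities.** At an assumed true rate of 8%, shares of 3.5/30 to 7/30 give 14.5% to 28.2%. At that rate passing is already an even chance (50.0%), and the shares have no support in this population.
- **A lower goal.** Removing the 7 haemorrhagic strokes gives 23/626 = 3.7%, which might suggest a 14% goal. That corrects one mismatch with the benchmark and ignores dissections and the NIHSS cut-off.
- **Robot-caused events cannot be separated.** Protocol 5.4 defines device-related events as caused or contributed to by the CorPath system, 5.8 has the committee adjudicate that relationship, and SAP 4.4.10 reports it. The breakdown is imperfect because the definitions of procedure-related disagree, but it exists.

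**What to change.** Before the periprocedural analysis described in Protocol 6.7, put one identical definition in the Protocol Summary, Protocol 3.3, Protocol 6.2 and SAP 4.3:

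1. Omit the robotic-cause condition, as both analysis sections already do.
2. State the NIHSS increase of at least 4 in SAP 4.3, and tie it to the assessment that Protocol 4.8.9 already requires at 24 hours or discharge, whichever is first.
3. Count haemorrhagic major stroke, as Protocol 6.2 and the benchmark do, and keep the 15% goal.
4. Report robot-caused events as a secondary breakdown using the adjudicated device relationship. First reconcile the meaning of procedure-related: Protocol 5.2 and 5.3 include events from any device used, whereas the Procedure-Related definition in SAP Appendix 1 excludes events associated with CorPath use.

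The cost is wording in four places and one reconciled definition, with no extra patients or visits. The reported rate may be slightly higher than under Protocol 3.3 or SAP 4.3. If the rate under the wider wording is the planned 5%, the chance of passing at n=108 is 90.8%, which still meets the planned 90%. It would be 80.0% at a true 6%.

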4.4 Secondary Endpoints

4.4.1 Secondary Endpoint 1: Clinical Outcome

Endpoint: Defined as the clinical outcome using the Modified Rankin Scale and/or occurrence of thromboembolic events and neurological deterioration assessed by NIHSS score change (NIHSS score change > 3). This endpoint is assessed at 90 and 180 day follow-up.

Subjects to Include: Analysis Cohort

Statistical Analysis: The count and proportion of subjects with each value of the Modified Rankin Scale will be calculated along with a 2-sided Clopper Pearson Exact 95% confidence interval. The count and proportion of subjects who experience a thromboembolic event AND neurological deterioration (NIHSS score change > 3) will be calculated along with a 2-sided Clopper Pearson Exact 95% confidence interval. CRF 5 Endovascular Procedure Patient Assessment has the baseline NIHSS score, while CRF 14 90-Day Follow-Up has the 90-day mRS, and CRF 15 180-Day Follow-Up has the 180-day mRS and NIHSS score).

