### 1.2 Background

Subarachnoid hemorrhage is a life-threatening form of stroke with an estimated fatality rate between 26 and 36%. In approximately 80% of cases, subarachnoid hemorrhage is caused by the rupture of an intracranial saccular aneurysm. Aneurysms occur when structural abnormalities in the walls of the cerebral arteries cause weakening, thinning, and out-pouching of the vessel wall. They are frequently located at bifurcations within the proximal circle of Willis and approximately 20-50% of such aneurysms eventually rupture. While the incidence of subarachnoid hemorrhage varies widely from country to country and may be as high as 15 to 20 per 100,000 in Finland and Japan, its overall worldwide incidence is estimated to be 9.1 per 100,000 persons. As many as 30,000 Americans are affected per year.

Patients who survive subarachnoid hemorrhage long enough to be stabilized medically may experience cerebral vasospasm, delayed cerebral ischemia, hydrocephalus, deep venous thrombosis, and numerous medical sequelae, along with long-lasting neuropsychological changes, loss of productive years, and diminished quality of life. They are also at serious risk of re-rupture, and therefore it is usually appropriate for them to undergo treatment to minimize aneurysmal recurrence or re-rupture.

Meanwhile, it has been estimated that the remaining 50% to 80% of intracranial aneurysms present in the general population never rupture. The prevalence of unruptured intracranial aneurysms (UIA) in the general adult population has been estimated at between 1% and 5%, based on autopsy studies. Many are asymptomatic and detected only as incidental findings during cerebral imaging for other conditions. Others may cause headaches, seizures, cranial nerve palsies, focal neurologic deficits, and distal embolic ischemic events.

Due to the severe consequences of aneurysmal rupture, once a UIA is detected, a decision must be made between managing the patient conservatively or treating the aneurysm to prevent future rupture. While current clinical evidence favors treatment for ruptured aneurysms, the

decision to intervene for UIA is less straightforward and must balance the risk-benefit profile of the available interventions against the risks and benefits of watchful waiting.

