#### 3.4 Secondary Endpoints

Several secondary endpoints will be examined in this trial, including the following:

- 1. Clinical Outcome** - Clinical outcome as measured by Modified Rankin Scale. This is assessed at 90-Day Follow-Up ( $\pm 14$  days) and 180-Day Follow-Up ( $\pm 30$  days from the procedure date);
- 2. Robotically Navigate Device to the Target Aneurysm** - Defined as successful advancement of devices to the target aneurysm robotically;
- 3. Robotically Navigate Device *into* the Target Aneurysm** - Defined as successful navigation of device into the target aneurysm robotically;
- 4. Robotically Deploy Therapeutic Device *into* Target Aneurysm** - Defined as successful deployment of therapeutic device into the target aneurysm robotically;
- 5. Overall Procedure Time** - Defined as the time measured from the insertion of the access sheath/catheter until the removal of the microcatheter;

6. **Robotic Procedure Time** - Defined as the time measured from the first device used robotically until the removal of the microcatheter;
7. **Fluoroscopy Time** - Total fluoroscopy utilized during the procedure as recorded by the Imaging System;
8. **Patient Radiation Exposure** - DAP (dose-area-product) and CD/AK (cumulative dose/air kerma) as recorded during the procedure;
9. **Contrast Volume** - Total contrast used during the procedure;
10. **Adverse Events** - All adverse events (AEs) from the start of the CorPath GRX procedure until the end of the study will be summarized.
11. **Thromboembolic Events** - Defined as rate of thromboembolic events occurring up to 180-days following the robotic-assisted procedure;
12. **Devices Used Robotically** - All devices used will be recorded as successful or unsuccessful in conjunction with the CorPath GRX System;
13. **Aneurysm Occlusion** - Angiographic assessment of aneurysm occlusion grade according to the Raymond-Roy classification scale, parent-vessel compromise, and occlusion durability as assessed from an independent core laboratory. This will be assessed post-procedure and at a 180-day follow-up.

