### 4.8.2 Baseline Date

The following baseline data should be collected for all subjects prior to the planned index procedure (usually routinely done for endovascular robotic procedure subjects with cerebral aneurysms):

- Patient Eligibility Criteria
- Head CT angiography or MR angiography
- Demographics
- Medical history
- Pre-endovascular Patient Assessment conducted by a trained person with appropriate qualifications to perform these evaluations:
  - Modified Rankin score
  - Raymond Grade for previously coiled aneurysms
  - National Institutes of Health Stroke Scale (NIHSS) scale
- Laboratory tests, if performed under standard hospital procedure, *should* be collected for all subjects prior to planned index-procedure (usually routinely done for patients undergoing cerebral aneurysm endovascular procedure \*):
  - Hemoglobin (HGB)
  - Hematocrit (HCT)
  - Activated Partial Thromboplastin Time (aPTT)
  - Platelet count
  - International Normalized Ratio (INR)
  - Pregnancy test
  - Serum creatinine
  - Glomerular Filtration Rate (GFR)

**\* Note:** Pre-endovascular Patient Assessment and laboratory tests must be within 7 days of index procedure. Female patients of child-bearing potential must have a negative pregnancy test (serum or urine).

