## 6.7 Endpoint Analysis and Reporting

All statistical analyses will be performed using SAS Version 9.4 or higher or other valid statistical software. Descriptive summary statistics will be provided for endpoints along with 95% confidence intervals as appropriate. Subject data listings and tabular and graphical presentations (e.g., bar graphs, pie charts, line graphs) of results may also be provided.

The secondary endpoint at the nominal 90 days post-procedure (modified Rankin Score) will be reported with descriptive statistics. Secondary endpoints captured at the nominal 180-day visit will be presented in tabular format (see Table 5) where appropriate; and for Clinical assessment & Physical Exam variables, with descriptive statistics; data for Target Aneurysm Assessment will be presented in a tabular format (see Table 1).

Adverse events occurring during or before the post procedure visit identified in Table 1 will be reported separately. Adverse events occurring after this visit will be reported (1) separately and (2) pooled with prior adverse events.

An analysis of periprocedural data will be performed upon completion of the post-procedure visit of the 108th enrollment and/or enrollments that have closed. The final analysis will be performed after follow-up is completed for all enrolled subjects. A separate statistical analysis plan (SAP) will be prepared and will include additional details for planned analyses.

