The Corindus CorPath GRX Neuro trial is a prospective, single-arm, international, multi-center, non-inferiority study to evaluate the effectiveness and safety of the CorPath GRX System for endovascular cerebral aneurysm embolization compared to historical controls. Subject selection requires a clinical indication for endovascular coil and/or stent-assist coiling embolization of cerebral aneurysms.

The CorPath GRX System is intended for use in the remote delivery and manipulation of interventional devices during percutaneous coronary and vascular procedures. The CorPath GRX System is designed to allow the operator to remotely manipulate interventional devices within a patient's vasculature to perform vascular procedures in a precise and well-controlled fashion, without being exposed to radiation levels typically encountered during a conventional (i.e., manual) procedure. The complete CorPath GRX System includes a bedside unit, interventional cockpit, and control console.

The recruitment phase is 18 months, follow-up is 180 days, and total study duration is 24 months. All subjects will be followed post-CorPath GRX endovascular embolization procedure through 180 days.

The subject population is subjects with a clinical indication for endovascular coil and/or stent-assisted coiling embolization of cerebral aneurysms. Up to 120 subjects will be enrolled in order to achieve at least 108 subjects in the study; each site will try to recruit a maximum of 20 subjects.

The data collection schedule is provided in Table 1 below.

Table 1. Data collection schedule

	Pre-procedure	Procedure	Post Procedure
			(24 hours post-procedure or hospital discharge)
Patient Eligibility Criteria	X		
Medical History	X ¹		
Head CT angiography or MRI angiography	X ¹		
Clinical assessment & Physical exam: including: 
• Hunt and Hess scale• Modified Rankin score• Raymond Grade for previously coiled aneurysms• National Institutes of Health Stroke Scale (NIHSS) scale• World Federation of Neurological Surgeons (WFNS) Subarachnoid Hemorrhage (SAH) Grade• Fisher grade	X ¹		X
Raymond Grade-Roy Occlusion Classification Scale	X ³		X
Laboratory Tests: complete blood count, hemoglobin, platelet count, platelet function testing, pregnancy test, serum creatinine and glomerular filtration rate.	X ^{1,2,4}		X ²
Procedure Parameters (CorPath GRX use, procedure time, fluoroscopy time, patient radiation exposure, etc.)		X	
Angiography		X ⁵	
Contrast volume		X	

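### SAP 4.4.1 reports 90- and 180-day mRS only as raw values, so the summary cannot show how much of the disability is new, although baseline mRS is collected

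*SAP*

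**What the plan says.** Protocol 3.4 defines the endpoint as "Clinical outcome as measured by Modified Rankin Scale", with no threshold and no reference to baseline. SAP 4.4.1 sets the analysis: "The count and proportion of subjects with each value of the Modified Rankin Scale will be calculated", with a two-sided Clopper-Pearson 95% interval, and "This endpoint is assessed at 90 and 180 day follow-up". Protocol 6.7 adds only that "The secondary endpoint at the nominal 90 days post-procedure (modified Rankin Score) will be reported with descriptive statistics". None of these sections plans a change score, a shift table or a definition of worsening.

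The design is a "prospective, single-arm, international, multi-center, non-inferiority study". None of the four inclusion criteria (protocol 4.6.1) or four exclusion criteria (4.6.2) limits baseline mRS.

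Protocol 4.8.2 lists "Modified Rankin score" in the pre-procedure assessment, and both the protocol's Schedule of Activities and SAP Table 1 schedule it. Protocol 4.8.9 requires it again within 24 hours or before discharge. SAP 4.4.1 names data sources for the 90-day mRS, the 180-day mRS and NIHSS, and the baseline NIHSS. It names none for baseline mRS.

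The same SAP section has one baseline-referenced component: the proportion of subjects with both a thromboembolic event and an NIHSS change above 3.

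**The concern.** A raw mRS distribution mixes disability the subject brought to the procedure with disability that appeared afterwards. A subject stable at mRS 2 and one who moved from 0 to 2 fall in the same row.

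In a randomised trial the control arm would carry a similar baseline mix. Here there is no control arm, and the historical tables (protocol 6.4, SAP 3.1) contain no mRS figures. The reader therefore has nothing against which to judge a raw percentage except the subjects' own starting point, and the analysis does not use it.

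Non-zero baseline mRS is possible in this population. Protocol 4.8.2 calls for "Raymond Grade for previously coiled aneurysms", so retreatment is foreseen. On unruptured aneurysms that are not silent, protocol 1.2 says "Others may cause headaches, seizures, cranial nerve palsies, focal neurologic deficits, and distal embolic ischemic events".

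At stake is what the late clinical-outcome table means. It depends partly on who was enrolled: it may present old disability as a poor result, or leave new disability unrecognisable among subjects who entered with some.

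**Working it through.** **The plan's own figure.** The mRS endpoint has no stated rate, threshold, sample size or power. The only figure borrowed here is N = 108, set by the effectiveness endpoint (80% goal, 90% expected, one-sided 0.025, 80% power; SAP 3.2). By normal approximation:

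N = [(1.960·√(0.80·0.20) + 0.842·√(0.90·0.10)) / 0.10]² = 107.4, rounded up to 108.

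The stated figure reproduces.

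**What separate tables can recover.** Suppose the final report also contained a stand-alone baseline mRS table. The protocol (6.8) and SAP (4.5) plan a baseline description, but neither names mRS in it. Fix any mRS level and let

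- n = subjects with both assessments,
- b = number at or above that level at baseline,
- k = number at or above it at follow-up.

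The number newly at or above the level is k minus those at or above it on both occasions. That overlap can be as large as min(b, k) or as small as max(0, b + k − n). Hence

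max(0, k − b) ≤ new ≤ min(k, n − b),

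and the upper limit is simply k whenever k ≤ n − b.

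**Numbers.** The documents give no mRS distribution, so every b and k below is an assumption, with n = 108.

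| b before | k after | raw % after | new, lower | new, upper |
|---|---|---|---|---|
| 0 | 8 | 7.4% | 8 (7.4%) | 8 (7.4%) |
| 3 | 8 | 7.4% | 5 (4.6%) | 8 (7.4%) |
| 5 | 8 | 7.4% | 3 (2.8%) | 8 (7.4%) |
| 8 | 8 | 7.4% | 0 (0%) | 8 (7.4%) |
| 5 | 11 | 10.2% | 6 (5.6%) | 11 (10.2%) |
| 11 | 11 | 10.2% | 0 (0%) | 11 (10.2%) |

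For b = 5 and k = 8, the Clopper-Pearson 95% interval for new disability is 0.6% to 7.9% if the true count is 3, and 3.3% to 14.1% if it is 8. These ends are logical limits, not equally likely values: the upper one requires all five initially disabled subjects to improve below the level. A paired table gives the exact count.

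The raw distribution alone, without a baseline table, allows anything from 0 to k. If nobody has baseline disability (first row), raw and new coincide and nothing is lost.

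**Whether another planned analysis supplies the mRS change.**

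- *NIHSS-change component (SAP 4.4.1).* It counts a subject only if a thromboembolic event also occurred, so disability from haemorrhage, for example, falls outside it. The 90-day contact is by telephone with only mRS required (Schedule of Activities, footnote 6). At 180 days only mRS is required and other scales are discretionary (footnote 8). The SAP names no source for a 90-day NIHSS.
- *Adverse events and adjudication (protocol 5.1 and 5.8, SAP 4.4.10).* These classify events and their relation to device or procedure. They do not produce a distribution of functional change.

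Neither replaces a paired mRS summary.

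**The case against.** The strongest reply is that the trial is not blind to new harm. Under protocol 5.1 a pre-existing condition becomes an adverse event only if it worsens or recurs. Events are recorded through 180 days and summarised by seriousness and relatedness. A Surveillance Committee of independent physicians adjudicates them and examines imaging against neurological deterioration. This stands. A reader might infer that the trial as a whole cannot tell old disability from new; the documents do not support that. The gap is confined to the mRS summary.

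A reader might also infer that pairing would separate the natural course of the disease from procedural harm. It would not. In a single arm, change from baseline shows that a subject worsened, not why. Attribution belongs to the relatedness assessment and adjudication.

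Nor does the plan hide worsening inside a favourable-outcome group. SAP 4.4.1 reports every mRS value and neither document plans a 0-to-2 grouping. A move from 0 to 2 would appear in the table; it could not be identified as new.

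Material baseline disability is not established either. Subjects have unruptured aneurysms, must be conscious and consenting, may not be under guardianship, and are screened by an Eligibility Committee. Protocol 1.2 notes that many unruptured aneurysms cause no symptoms. The effect could be small, and the documents do not say.

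Finally, the 90-day mRS is taken by telephone, whereas the baseline value comes from a pre-procedure assessment by a trained person. A one-point change may partly reflect the mode of assessment, so it should not be the sole headline.

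**Conclusion.** The point holds for the mRS summary in SAP 4.4.1. With one arm, no baseline limit and no mRS benchmark, the count at each value cannot show how much disability is new. A separate baseline table would narrow this only to the range from max(0, k − b) to k, for example 3 to 8 of 108 when b = 5 and k = 8. The size in this trial is unknown: it grows with the number of subjects disabled at entry and is nil if there are none.

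This is a worthwhile improvement to a descriptive secondary endpoint with no hypothesis or success rule. A reader might infer that it weakens the primary conclusions, but both primary endpoints are analysed without mRS, and the sample size does not depend on it.

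**What to change.** In SAP 4.4.1:

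1. Name the case report form that supplies baseline mRS.
2. Add baseline-by-90-day and baseline-by-180-day mRS shift tables, with death scored 6.
3. Prespecify the proportion of subjects whose mRS is worse than baseline at each visit, with a Clopper-Pearson 95% interval. State the paired denominator (baseline value and follow-up value or death) and the number without a pair.
4. Keep the planned raw distribution alongside.
5. Note that the 90-day value is by telephone, so a one-point change needs caution, and that the tables separate old from new disability without attributing cause.

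The cost is SAP wording and one additional paired table per visit, from data already collected. No visit, assessment or sample-size change is needed. The table could be built later from the same data, but specifying it now prevents the definition of worsening from being chosen with results in view.
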